### Objective(s)/Endpoints:

Objectives	Endpoints

Primary
 
 
To investigate the efficacy of LY3209590 arms in study participants with T2DM
 
	
 
HbA1c change from baseline to Week 32
 

Secondary
 
Efficacy:
 
 
To investigate the efficacy of LY3209590 compared with insulin degludec in study participants with T2DM
 
 
Safety:
 
 
To investigate the safety of LY3209590 compared with insulin degludec in study participants with T2DM
 
 
Pharmacokinetics:
 
 
To characterize the PK of LY3209590 in study participants with T2DM
 
	
 
HbA1c change from baseline to Week 12 and 32
 
Fasting glucose change from baseline to Weeks 12 and 32
 
Insulin dose change from baseline to week 12 and 32
 
Incidence and Rate of nocturnal and documented symptomatic hypoglycemia events during the treatment period
 
Incidence of treatment-emergent serious adverse events
 
Body weight change from baseline at Weeks 12 and 32
 
LY3209590 population-based parameters, such as, AUC within dosing interval at Weeks 12 and 32
 

Abbreviations: AUC = area under the curve; HbA1c = hemoglobin A1c; PK = pharmacokinetics; T2DM = type 2 diabetes mellitus

[figure not shown]

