**Table BDCM.2. Objectives and Endpoints**

Objectives	Endpoints
Primary 
 
To investigate the efficacy of LY3209590 arms in study participants with T2DM
 
	
 
HbA1c change from baseline to Week 32
 

Secondary Efficacy 
 
To investigate the efficacy of LY3209590 compared with insulin degludec in study participants with T2DM.
 
	
 
HbA1c change from baseline to Week 12 and 32
 
Fasting glucose change from baseline to Weeks 12 and 32
 
Insulin dose change from baseline to week 12 and 32
 

Safety 
 
To investigate the safety of LY3209590 compared with insulin degludec in study participants with T2DM.
 
	
 
Incidence and rate of hypoglycemia
 
Incidence and rate of nocturnal hypoglycemia
 
Incidence and rate of severe hypoglycemia
 
Incidence of treatment-emergent serious AEs
 
Body weight change from baseline at Weeks 12 and 32
 

Pharmacokinetics 
 
To characterize the PK of LY3209590 in study participants with T2DM
 
	
 
LY3209590 population-based parameters, such as, AUC within dosing interval at Weeks 12 and 32
 

Exploratory 
 
To investigate the safety and tolerability of LY3209590 compared with insulin degludec in study participants with T2DM.
 
	
 
Treatment-emergent AEs
 
Discontinuation of IP due to AEs
 
Clinical laboratory results
 
Systematic assessment of injection site reactions
 
Insulin dose during follow up period
 
Incidence and rate of hypoglycemia during treatment and follow-up period
 
Incidence and rate of daytime hypoglycemia
 
Liver aminotransferase change from baseline to Weeks 12 and 32
 

 
To explore quality of glycemetic control compared with insulin degludec using CGM
 
	
 
Glucose time in target range, time in hyperglycemia, time in hypoglycemia
 
Duration and recurrence of hypoglycemic events
 

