## 9.2.2. Adverse Events of Special Interest

### 9.2.2.1. Hypoglycemia

Study participants will collect information on episodes of hypoglycemia starting from Visit 2 until the last study visit (Visit 801 or ET visit). For that purpose, study participants will be trained about signs and symptoms of hypoglycemia, how to treat hypoglycemia, and how to collect in study diary appropriate information for each episode of hypoglycemia according to the Schedule of Activities (Section 2). Site personnel will enter this information into the eCRF at visits indicated in the Schedule of Activities (Section 2).

Investigators should use the following definitions and criteria when diagnosing and categorizing an episode considered to be related to hypoglycemia (the PG values in this section refer to values determined by a laboratory or International Federation of Clinical Chemistry and Laboratory Medicine plasma-equivalent glucose meters and strips) (American Diabetes Association 2005):

- **Documented symptomatic hypoglycemia** is defined as any time a study participant feels that he/she is experiencing symptoms and/or signs associated with hypoglycemia, and has a PG level of  $\leq 70$  mg/dL ( $\leq 3.9$  mmol/L).
- **Asymptomatic hypoglycemia** is defined as any event not accompanied by typical symptoms of hypoglycemia but with a measured PG  $\leq 70$  mg/dL ( $\leq 3.9$  mmol/L).
- **Probable symptomatic hypoglycemia** is defined as an event during which symptoms of hypoglycemia are not accompanied by a PG determination (but that was presumably caused by a PG concentration  $\leq 70$  mg/dL [ $\leq 3.9$  mmol/L]).
- **Severe hypoglycemia** is defined as an episode requiring the assistance of another person to actively administer carbohydrate, glucagon, or other resuscitative actions. These episodes may be associated with sufficient neuroglycopenia to induce seizure or coma. Plasma glucose measurements may not be available during such an event, but neurological recovery attributable to the restoration of PG to normal is considered sufficient evidence that the event was induced by a low PG concentration.
- **Nocturnal hypoglycemia** is defined as any hypoglycemic event that occurs between bedtime and waking.
- **Total hypoglycemia** is defined as any event meeting the criteria for documented symptomatic hypoglycemia, asymptomatic hypoglycemia, or probable symptomatic hypoglycemia

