#### **10.3.4.3. Hypoglycemia Episodes**

The rate and incidence analyses will be analyzed. Details will be provided in the SAP. Statistical analysis will be performed for overall total hypoglycemia, documented symptomatic hypoglycemia and nocturnal hypoglycemia. Listing of hypoglycemic episodes and severe hypoglycemic episodes will be presented by visit for each study participant. If a sufficient number of severe hypoglycemic episodes are reported, then incidence summaries and analysis similar to incidence of hypoglycemic episodes will be included.

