3.2.2. Safety

To compare the safety of LY3209590 versus insulin Degludec treatment groups for the following:

1. Documented, documented nocturnal and severe hypoglycemia incidence and rates during the treatment period (0-12, 12-32, and 0-32 weeks);
2. Treatment-emergent serious adverse events (SAEs) incidences;
3. Body weight change from baseline at Week 12 and 32.

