4.10.3.2. Hypoglycemia Events

Both the rate per 1 patient year and incidence of the following type of hypoglycemia events will be derived and analyzed: documented hypoglycemia, documented nocturnal hypoglycemia (occurs between bedtime and waking), and documented non-nocturnal hypoglycemia (occurs between waking and bedtime).

[Table BDCM.1](#) provides the summary of statistical method for hypoglycemia event related analysis. Additionally, severe hypoglycemia events will be listed, and incidence of severe hypoglycemia will be compared between treatments using Fishers' exact test.

Table BDCM.1. Hypoglycemia Event Related Analyses

Endpoint	Time Point*	Statistical Method
Rate of hypoglycemia events defined by glucose <54 mg/dL (3.0 mmol/L) and ≤ 70 mg/dL (3.9 mmol/L) 
 • Documented • Nocturnal • Non-Nocturnal 	0-12, 0-32, 12-32 weeks, post-treatment period (up to Visit 801)*	Negative binomial regression with treatment, baseline SU use (yes/no), baseline HbA1c, baseline hypoglycemia event rate with the same category of the dependent variable, log (exposure in year) as the offset in the model.
Incidence of hypoglycemia events defined by glucose <54 mg/dL (3.0 mmol/L) and ≤ 70 mg/dL (3.9 mmol/L) 
 • Documented • Nocturnal • Non-Nocturnal 	0-12, 0-32, 12-32 weeks, post-treatment period (up to Visit 801)*	Logistic regression with treatment, baseline SU use (yes/no), baseline HbA1c, baseline hypoglycemia event rate with the same category of the dependent variable in the model. Note that the logistic regression will be conducted when ≥10 patients with this event.

 • Proportion of patients with HbA1c <7% without nocturnal hypoglycemia event • Proportion of patients with HbA1c ≤6.5% without nocturnal hypoglycemia event 	0-32 weeks	Logistic regression with treatment, baseline SU/meglitinide use (yes/no), baseline HbA1c, and baseline nocturnal hypoglycemia event rate in the model.

Abbreviations: HbA1c = hemoglobin A1c.

Note: The hypoglycemia rate per year during defined period is calculated by the number of hypoglycemia within the period/number of days patient at risk within the period*365.25 days. The hypoglycemia incidence during defined period indicates if the patient has at least 1 hypoglycemia events within the period (Yes/No). The baseline hypoglycemia rate is the rate calculated between Visit 1 and Visit 3.

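### The SAP gives no analysis of total hypoglycemia or of the severe hypoglycemia rate, and leaves open whether its documented category is the protocol's documented symptomatic one

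*Protocol*

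**What the plan says.** **Protocol.** Section 10.3.4.3 opens with "The rate and incidence analyses will be analyzed. Details will be provided in the SAP" and then names the categories: "Statistical analysis will be performed for overall total hypoglycemia, documented symptomatic hypoglycemia and nocturnal hypoglycemia". For severe events it plans listings and adds a condition: "If a sufficient number of severe hypoglycemic episodes are reported, then incidence summaries and analysis similar to incidence of hypoglycemic episodes will be included".

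The two endpoint lists differ. The synopsis has "Incidence and Rate of nocturnal and documented symptomatic hypoglycemia events during the treatment period". Protocol Table BDCM.2 has unqualified hypoglycemia, nocturnal hypoglycemia and "Incidence and rate of severe hypoglycemia"; among its secondary safety endpoints it names neither documented symptomatic nor total events.

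Section 9.2.2.1 defines the categories. Documented symptomatic hypoglycemia "is defined as any time a study participant feels that he/she is experiencing symptoms and/or signs associated with hypoglycemia" and also needs a plasma glucose of 70 mg/dL or less. Asymptomatic events have the same glucose value without symptoms. Probable symptomatic events have symptoms but no glucose measurement. Total hypoglycemia is the union of these three. Nocturnal covers any event between bedtime and waking.

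**SAP.** The secondary safety objective in 3.2.2 is "Documented, documented nocturnal and severe hypoglycemia incidence and rates during the treatment period". Section 4.10.3.2 then analyses rate and incidence of "documented hypoglycemia, documented nocturnal hypoglycemia (occurs between bedtime and waking), and documented non-nocturnal hypoglycemia (occurs between waking and bedtime". SAP Table BDCM.1 assigns negative binomial regression to rates and logistic regression to incidence, at <54 and ≤70 mg/dL. Severe events are listed, and their incidence is compared with Fisher's exact test.

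**Rule on changes.** Protocol 10.3.1 and SAP 4.1 allow changes to non-principal analyses without a protocol amendment, provided that the change and its justification are described in the SAP and/or the clinical study report.

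**The concern.** Hypoglycemia is the downside that protocol 3.2 singles out for a once-weekly insulin, and protocol 7.8.2.2 says that assessing it is an objective of the study. If the SAP is followed as written, some of the promised analyses of that risk will not be produced.

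The symptom criterion matters in this design. The trial is open-label and every participant wears an unblinded glucose monitor with alarms. Protocol 9.4.4 tells participants to record hypoglycemia-related monitor readings in their diaries, so low readings without symptoms could enter the event data. Monitor-determined hypoglycemia already has its own analysis in SAP 4.11. What the symptomatic category adds is the event as the participant experienced it.

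A category with no stated symptom rule can also be given its meaning after open-label data have been seen.

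**Working it through.** No figure in the plan bears on this point, so the check compares texts.

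**Step 1. Notation from protocol 9.2.2.1.**
- S = documented symptomatic (symptoms, glucose ≤70 mg/dL)
- A = asymptomatic (no symptoms, glucose ≤70 mg/dL)
- P = probable symptomatic (symptoms, no glucose value)
- Total = S + A + P

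**Step 2. The SAP's documented category at ≤70 mg/dL, called D.** The SAP permits two readings.
- Glucose only: D = S + A, so Total − D = P, and S has no analysis of its own.
- Glucose plus symptoms: D = S, so Total − D = A + P, and S is analysed.

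Either way D is not total hypoglycemia. The two coincide only if the missing components happen to be empty (P on the glucose-only reading, both A and P on the other). The nocturnal and non-nocturnal rows do not close the gap, because SAP 4.10.3.2 restricts both to documented events.

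**Step 3. Promised against planned.**
- Total, rate and incidence (protocol 10.3.4.3): no SAP analysis.
- Documented symptomatic, rate and incidence (protocol synopsis and 10.3.4.3): analysed only if D requires symptoms.
- Nocturnal, rate and incidence (synopsis, protocol Table BDCM.2 and 10.3.4.3): modelled, but narrowed from any event to documented events.
- Severe incidence (protocol Table BDCM.2, SAP 3.2.2): Fisher's exact test and listing.
- Severe rate (protocol Table BDCM.2, SAP 3.2.2): no SAP analysis. The note to SAP Table BDCM.1 gives a general formula for a yearly rate, but no row applies it to severe events.

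**Step 4. Is the change explained?** SAP 4.10.3.2 gives no rationale. The SAP's revision history lists the main changes since its version 1 and does not mention hypoglycemia categories.

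**Step 5. How precise could a severe rate be?** With 125 randomized per arm, and if all stayed for 32 weeks, patient-time per arm is at most 125 × (32 × 7) / 365.25 = 76.7 patient-years. At the SAP's two-sided 90% level, the exact Poisson upper limit for zero events is −ln(0.05) = 3.00 events. That is 3.00 / 76.7 × 100 = 3.9 per 100 patient-years. Dropout shortens patient-time and raises this limit.

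**The case against.** **Documented may be shorthand.** In the protocol's event definitions, the word labels only one category, documented symptomatic, and the ≤70 mg/dL threshold is the same. A reader might infer that the SAP has dropped that endpoint outright. The documents do not support this. The table describes its events by glucose value, which leans towards a glucose-only reading, but it neither requires nor waives symptoms. This part of the objection stands.

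**The protocol disagrees with itself.** SAP 3.2.2 closely follows protocol Table BDCM.2, which names neither documented symptomatic nor total events as secondary endpoints. So it would be too broad to say that the named safety endpoints go unanalysed: nocturnal rate and incidence and severe incidence are covered. The mismatch with protocol 10.3.4.3 remains, because that section promises analyses of both categories.

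**Severe events.** Protocol 10.3.4.3 asks for no severe rate, and the SAP's Fisher test goes beyond that section's conditional wording. Severe events are also reported as serious adverse events, and SAP 4.10.1 sums patient-years. Events may be few, since exclusion criterion 13 removes people with a severe episode in the previous 6 months. All of that is fair. But the rate is an endpoint in protocol Table BDCM.2 and an objective in SAP 3.2.2, so the SAP sets an objective that it does not analyse.

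**Changes are allowed.** They are, if described and justified. A study report could still do this, but the SAP does not.

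**Dilution.** A reader might infer that asymptomatic alarm readings will hide a difference in symptomatic events. The documents give no share of asymptomatic events and do not establish how many such readings would reach SAP Table BDCM.1; protocol 9.2.2.1 refers to laboratory or meter glucose. Purely as illustration, suppose a glucose-only category, a symptomatic rate ratio of 1.5, and half of comparator-arm events symptomatic. With no arm difference in asymptomatic events, the ratio would show as 0.5 × 1.5 + 0.5 × 1.0 = 1.25. If asymptomatic events rose in the same proportion, it would stay at 1.5. No dilution figure can be drawn from the plan.

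**Conclusion.** The concern holds in a bounded form. Two gaps do not depend on interpretation: total hypoglycemia is not analysed as the protocol defines it, and the severe rate has no analysis although the SAP itself lists it as an objective. A third is conditional: documented symptomatic hypoglycemia lacks an analysis only if the SAP's documented category ignores symptoms.

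The size is best stated as analyses missing rather than as bias, because the documents contain no event rates. The first two conclusions rest on the definitions in protocol 9.2.2.1 and on SAP Table BDCM.1 being the full list of modelled categories. This should be corrected: it is more than missing detail, since running the SAP as written would leave promised analyses of the drug's main risk undone without explanation.

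**What to change.** - State in SAP 4.10.3.2 whether documented requires symptoms.
- Add total hypoglycemia to SAP Table BDCM.1, using the 9.2.2.1 definition and the existing negative binomial and logistic models. A glucose-threshold row cannot hold it, since part of the category has no glucose value.
- Add documented symptomatic hypoglycemia in the same way, unless the clarified documented category already is that category.
- Report severe events per 100 patient-years by arm with exact Poisson intervals, beside the Fisher test.
- Align the protocol synopsis, protocol Table BDCM.2, protocol 10.3.4.3, SAP 3.2.2 and SAP 4.10.3.2. If a category is to be dropped, record that and give the reason.

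The cost is a few extra table rows. Sites already categorise events and enter them in the eCRF, and patient-years are already computed. The severe rates will probably be imprecise and should be read as descriptive.

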#### **10.3.4.4. Laboratory Measures**

Summary statistics will be provided for laboratory measures, by treatment group and by visit.

A listing of laboratory measurements for individual study participants will be presented by visit. An additional listing will be presented for all laboratory measurements that are outside the normal range.

Descriptive statistics for the laboratory analyses will be presented by treatment group and visit, including safety off-treatment visits.

Laboratory analyses with categorical responses will be summarized by visit and treatment group using frequency and percentage.

The maximum/minimum post-baseline observation (as applicable for a laboratory) will be compared to the baseline observation by examining the proportion of study participants whose test values are within and outside the reference ranges.

#### **10.3.4.5. Electrocardiograms**

A listing of the individual and averaged ECG measurements, by study participant, will be produced. This will include the time elapsed between the onset of ventricular depolarization and the end of ventricular repolarization (QT) corrected values described below.

Descriptive statistics for the absolute measurements, outliers, and changes from baseline for selected ECG parameters will be presented by treatment arm. These include the ECG heart rate, and the following intervals: QT and QT corrected for heart rate using Fridericia's formula (QTcF).

In addition, LY3209590 concentration-response analysis of QTcF results will be performed as well as a categorical analysis of absolute and change from baseline QTc intervals. Any additional ECG analyses will be detailed in the SAP.

#### **10.3.4.6. Adverse Events of Special Interest**

Hypoglycemia, major adverse cardiovascular events, and injection site reaction are defined as AESIs.

Descriptive statistics for the AESIs will be presented by treatment group and visit. Continuous responses will be summarized using sample size, mean, SD, median, minimum, and maximum, while categorical responses will be summarized using frequencies and percentages.

If necessary, continuous AESIs will be analyzed using a similar MMRM-based model.

Categorical AESIs will be analyzed using a logistic regression analysis with fixed effects of treatment, and HbA1c strata.

### **10.3.5. Pharmacokinetic/Pharmacodynamic Analyses**

LY3209590 concentration data will be analyzed using a population PK approach via nonlinear mixed-effects modeling with the NONMEM software. The relationships between LY3209590 and/or concentration and efficacy, tolerability, and safety as well as biomarker endpoints will be characterized if exploratory analyses of the PD data warrant further PK/PD analyses upon review. Such analyses may include, but are not necessarily limited to, glucose, HbA1c, QTc, hypoglycemia, and vital signs.

In addition, if population PK and PK/PD models can be established, the impact of additional subject factors, such as age, weight, gender and renal function on PK and/or PD parameters, may be examined. Should ADA be detected from immunogenicity testing, its impact on LY3209590 PK or any relevant PD parameters will also be examined.

### **10.3.6. Evaluation of Immunogenicity**

The frequency of antibody formation to LY3209590 will be determined. Treatment-emergent ADA are defined as those with a titer 2-fold (1 dilution) greater than the minimum required dilution if no ADAs were detected at baseline (treatment-induced ADA) or those with a 4-fold (2 dilutions) increase in titer compared to baseline if ADAs were detected at baseline (treatment-boosted ADA). For the TE ADA+ study participants, the distribution of maximum titers will be described.

The relationship between the presence of antibodies, antibody titers, and clinical parameters (for example, AEs, efficacy measures) may be assessed.

### **10.3.7. Other Analyses**

Detailed analysis plan for CGM will be documented in SAP.

#### **10.3.7.1. Health Economics**

Not applicable.

#### **10.3.7.2. Subgroup Analyses**

Subgroup analyses of important factors, including age, race, ethnicity, gender, duration of diabetes, baseline HbA1c ( $<8.5\%$ ,  $\geq 8.5\%$ ), BMI, and other factors to be specified in the SAP are planned for the key outcomes of HbA1c, insulin dose and incidence and rate of hypoglycemia.

These will be conducted using the analysis of covariance model with strata, treatment, factor, treatment-by-factor interaction as fixed effects, and baseline as covariate.

Covariate analysis of PK and PK/PD may be performed.

Other exploratory subgroup analyses may be performed as deemed appropriate.

### **10.3.8. Interim Analyses**

Interim analyses have been planned for this study. The cancellation or addition of interim analysis will be determined at any time during the study and does not need protocol amendment.

An interim analysis of select safety, efficacy, and PK data is planned when approximately 50% of study participants complete 6 weeks of treatment. Results of interim analysis might be used for adjusting LY3209590 dosing algorithm.

A subsequent interim analysis of select safety, efficacy, and PK data is planned when all study participants complete 12 weeks of treatment. Results of interim analysis will be used to design subsequent studies.

In addition, the study team will perform periodic safety reviews during the study and if safety signals or concerns arise from these reviews, safety data may need to be in an unplanned interim analysis.

Study sites will receive information about interim results ONLY if they need to know for the safety of their study participants.

## 12. Appendices

---

## Appendix 1. Abbreviations and Definitions

---

Term	Definition
ADA	antidrug antibodies
AE	adverse event: Any untoward medical occurrence in a study participant or clinical investigation subject administered a pharmaceutical product that does not necessarily have a causal relationship with this treatment. An adverse event can therefore be any unfavorable and unintended sign (including an abnormal laboratory finding), symptom, or disease temporally associated with the use of a medicinal (investigational) product, whether or not related to the medicinal (investigational) product.
AESI	adverse event of special interest
ALP	alkaline phosphate
ALT/SGPT	alanine aminotransferase/ serum glutamic pyruvic transaminase
AST/SGOT	aspartate aminotransferase/ serum glutamic oxaloacetic transaminase
AUC	area under the curve
blinding/masking	
A single-blind study is one in which the investigator and/or his staff are aware of the treatment but the study participant is not, or vice versa, or when the sponsor is aware of the treatment but the investigator and/his staff and the study participant are not.
 
A double-blind study is one in which neither the [study participant/subject] nor any of the investigator or sponsor staff who are involved in the treatment or clinical evaluation of the subjects are aware of the treatment received.

BMI	body mass index
BP	blood pressure
CGM	continuing glucose monitoring
Complaint	A complaint is any written, electronic, or oral communication that alleges deficiencies related to the identity, quality, purity, durability, reliability, safety or effectiveness, or performance of a drug or drug delivery system.
CRP	clinical research physician: individual responsible for the medical conduct of the study. Responsibilities of the CRP may be performed by a physician, clinical research scientist, global safety physician or other medical officer.
CSR	clinical study report
CV	cardiovascular
DPP-4	dipeptidyl peptidase-4

---

ECG	electrocardiogram
eCRF	electronic case report form
Enroll	The act of assigning a study participant to a treatment. Study participants who are enrolled in the trial are those who have been assigned to a treatment.
Enter	Study participants entered into a trial are those who sign the informed consent form directly or through their legally acceptable representatives.
ERB	Ethics Review Board
ET	early termination
FAS	full analysis set
FBG	fasting blood glucose
FBS	Fasting blood sugar
FPG	fasting plasma glucose
GCP	good clinical practice
GGT	gamma-glutamyl transferase
HbA1c	hemoglobin A1c
ICF	informed consent form
interim analysis	An interim analysis is an analysis of clinical study data, separated into treatment groups, that is conducted before the final reporting database is created/locked.
investigational product (IP)	A pharmaceutical form of an active ingredient or placebo being tested or used as a reference in a clinical trial, including products already on the market when used or assembled (formulated or packaged) in a way different from the authorized form, or marketed products used for an unauthorized indication, or marketed products used to gain further information about the authorized form.
IWRS	interactive web-response system
LS	least squares
LY	LY3209590
MAD	multiple ascending dose
MMRM	mixed-effect model repeated measures
NAFLD	non-alcoholic fatty liver disease
OAM	oral antihyperglycemic medication
OTC	over the counter

---

---

PD	pharmacodynamic
PG	plasma glucose
PK	pharmacokinetics
PP	per-protocol set: The set of data generated by the subset of study participants who sufficiently complied with the protocol to ensure that these data would be likely to exhibit the effects of treatment, according to the underlying scientific model.
QTc	corrected QT interval
QTcF	QT corrected for heart rate using Fridericia's formula
SAD	single-ascending dose
SAE	serious adverse event
SAP	Statistical analysis plan
SC	subcutaneous
SD	standard deviation
SGLT	sodium-glucose cotransporter
SMBG	self-monitoring of blood glucose
SMPG	self-monitored plasma glucose
SU	sulfonylureas
SUSARs	suspected unexpected serious adverse reactions
Screen	The act of determining if an individual meets minimum requirements to become part of a pool of potential candidates for participation in a clinical study.
T2DM	type 2 diabetes mellitus
TEAE	treatment-emergent adverse event: An untoward medical occurrence that emerges during a defined treatment period, having been absent pretreatment, or worsens relative to the pretreatment state, which and does not necessarily have to have a causal relationship with this treatment.
ULN	upper limit of normal

---

---

